1 PROTOCOL SYNOPSIS

This Post Approval Study is a multi-center, prospective, open label, single arm cohort study to evaluate the long-term safety, long-term effectiveness, and survival rate in subjects implanted with the **remedē** System from the **remedē** System Pivotal Trial. Up to 94 subjects will be enrolled at up to 21 sites in the United States (US) and five (5) sites in the European Union (EU).

Only subjects who were implanted and actively being followed as part of the **remedē** System Pivotal Trial are eligible for this trial.

An individual subject's participation is expected to continue to five years post **remedē** System implant. Subjects will start follow-up at the appropriate follow-up visit based on their initial **remedē** System implant date. Subjects will be seen for an in-office visit at 36, 48, and 60 months post implant for a **remedē** System assessment, an assessment of medical stability, sleep study (polygram [PG] at 36- and 48-month visits and polysomnogram [PSG] at the 60-month visit), Epworth Sleepiness Scale (ESS) completion, and adverse event monitoring. Subjects will be contacted by phone at 30, 42, and 54 months post implant for survival and adverse event monitoring.

Data analyses will include an evaluation of long-term safety, long-term effectiveness, and survival rate.

2 STUDY PURPOSE AND JUSTIFICATION

This extended follow-up study is a Food and Drug Administration (FDA) condition of approval of the **remedē** System in adult patients with moderate to severe central sleep apnea (CSA). The primary purpose of this prospective, multicenter, single arm cohort study is to evaluate the long-term safety, long-term effectiveness, and survival rate in subjects implanted with the **remedē** System in the **remedē** System Pivotal Trial.

3 STUDY MILESTONES AND TIMELINE

Following FDA approval of the protocol, **remedē** System Pivotal Trial sites with active subjects will be invited to participate in this study. Activation of sites should be complete within six months following FDA approval of the protocol. Enrollment of subjects, defined as signing the informed consent, should be complete within six months following site activation.

Follow-up is planned for five years from the date of implant. Since all subjects have already completed 24 months of follow-up, total study duration is estimated to be three years.

4 BACKGROUND

4.1 Regulatory History

The **remedē** System Pivotal Trial demonstrated that **remedē** System therapy effectively treats CSA and delivers statistically significant and clinically meaningful improvements in sleep, respiratory, and patient-centered metrics. The primary effectiveness endpoint of the **remedē** System Pivotal Trial was met: a significantly higher proportion of subjects in the treatment group (35 of 68, 51%) had a 50% or higher reduction in Apnea-Hypopnea Index (AHI) from baseline to 6 months of follow-up than in the control group (8 of 73, 11%). The difference between groups was 41% ($p \leq .0001$). This significant difference demonstrated the superiority of **remedē** System therapy compared to no therapy. In the per protocol population, 60% of the Treatment subjects achieved a $\geq 50\%$ reduction in AHI versus 11% in the Control group. The benefits experienced by the Treatment group continued throughout the course of the study, demonstrating durability of effect, and were confirmed by the results of the Control group after 6 months of active therapy. In addition to the benefits conferred by meeting the primary effectiveness endpoint, all of the hierarchically tested secondary endpoints (Central Apnea Index [CAI], AHI, Oxygen Desaturation Index 4% [ODI4], percent sleep time in Rapid Eye Movement [REM], Patient Global Assessment [PGA], Arousal Index [AriI], and ESS) were met. The therapy was well tolerated, and 91% of subjects were free from serious adverse events (SAEs) related to the implant procedure, **remedē** System, or delivered therapy through 12 months indicating both procedural and chronic safety of the **remedē** System.

The **remedē** System received CE Mark approval on August 13, 2010.

The **remedē** System was approved for marketing in the US by the FDA on October 6, 2017. As a condition of approval, the Post Approval Study will continue to gather clinical evidence regarding the safety and effectiveness for the **remedē** System in adult subjects with moderate to severe CSA.

5 DEVICE NAME, INTENDED USE, AND SYSTEM DESCRIPTION

5.1 Device Name

The **remedē**[®] System

5.2 Indications for Use

The **remedē** System is an implantable phrenic nerve stimulator indicated for the treatment of moderate to severe CSA in adult patients.

5.3 System Overview

The system consists of an implantable pulse generator (IPG), one transvenous lead to stimulate the phrenic nerve, and one transvenous sensing lead to sense respiration via

transthoracic impedance. External, non-implanted devices and accessories of the **remedē** System include the **remedē** System programmer, external IPG, and programming wand. A detailed description of the **remedē** System can be found in the **remedē** System Implant and Clinician Use Manual found in [Appendix F](#).

6 STUDY DESIGN AND SCOPE

This is a multi-center, prospective, open label, single cohort study to evaluate the long-term safety, long-term effectiveness, and survival rate in subjects implanted with the **remedē** System in the **remedē** System Pivotal Trial. Up to 94 subjects will be enrolled at up to 21 US sites and 5 EU sites.

Only subjects who were implanted and actively being followed as part of the **remedē** System Pivotal Trial are eligible for this trial.

An individual subject's participation is expected to continue through five years post **remedē** System implant. Subjects will be seen for an in-office visit at 36, 48, and 60 months post implant for a **remedē** System assessment, an assessment of medical stability, sleep study (polygram [PG] at 36- and 48-month visits and polysomnogram [PSG] at the 60-month visit), Epworth Sleepiness Scale (ESS) completion, and adverse event monitoring. Subjects will be contacted by phone at 30, 42, and 54 months post implant for survival and adverse event monitoring. See [Table 1](#) Follow-up Schedule.

7 STUDY OBJECTIVES

1. Evaluate the survival rate

This endpoint is an assessment of survival in subjects with moderate to severe CSA being treated with the **remedē** System. Survival will be compared to historical controls or newly published results at three and five years post implant. No formal statistical hypothesis will be tested.

2. Evaluate long-term three and five-year device-related Serious Adverse Events (SAEs)

This endpoint is an assessment of long-term safety via summary of anticipated or unanticipated device-related SAEs. Events must meet the definition of serious as defined in [Section 10.8](#). Device-related SAEs include device explants due to device-related infection and events such as: device malfunction, lead fracture, lead component failure, lead dislodgment, lead displacement, pocket perforation, or extra-respiratory sensation requiring lead revision. **remedē** System IPG replacement for battery depletion will not be considered a device-related SAE unless it is earlier than anticipated. The number of events and subjects with an

event will be summarized through each time point. No formal statistical hypothesis will be tested.

3. Evaluate long-term three and five-year therapy-related SAEs

This endpoint assesses the safety of the **remedē** System by evaluating anticipated or unanticipated therapy-related SAEs. Therapy-related SAEs must meet the definition of a SAE as defined in [Section 10.8](#) and include events such as diaphragmatic stimulation discomfort, extra-respiratory stimulation, or concomitant device interaction. The number of events and subjects with an event will be summarized through each time point. No formal statistical hypothesis will be tested.

4. Evaluate the AHI, CAI, and obstructive apnea index (OAI) at three years using in-home polygram (PG) and at five years using in-lab polysomnogram (PSG)

This effectiveness endpoint will be assessed by summarizing the AHI, CAI, and OAI at three and five years, as well as change from baseline at five years. No formal statistical hypothesis will be tested.

5. Evaluate the change in quality of life from baseline to three and five years using the ESS

The ESS is a validated instrument that assesses a subject's daytime sleepiness. The objective is to demonstrate a reduction in the ESS score from baseline at three and five years. No formal statistical hypothesis will be tested.

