11 STATISTICAL METHODS

11.1 General Statistical Considerations

Data from this study will be combined with data from the **remedē** System Pivotal Trial. All subjects will be pooled for analysis regardless of original randomization assignment.

Descriptive statistics will be used to summarize data. Continuous variables will be summarized using means, standard deviations, medians, interquartile ranges, minimums and maximums. Categorical variables will be summarized by calculating the percent of subjects in each category. No imputation for missing data will be performed.

Statistical analyses will be performed using validated software (e.g., SAS).

Copies of databases used to prepare clinical report summaries will be archived to enable any statistical analyses performed to be replicated.

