11.2 Analysis Population

Intention-to-Treat (ITT): Subjects who were previously consented and randomized in the **remedē** System Pivotal Trial. All effectiveness and safety evaluations will be based on the ITT population. Effectiveness analyses will only include subjects with data at the visit of interest.

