11.3 Data Analyses

All subjects randomized in the **remedē** System Pivotal Trial will be included in the safety assessments, unless otherwise noted. All adverse events will be summarized by seriousness, relatedness, and temporal relationship to the procedure and will be analyzed in a descriptive fashion. The number of events and number of subjects experiencing events will be summarized.

The survival distribution will be estimated with a Kaplan-Meier curve and the 95% confidence interval for the three and five year (or other time point of interest) survival rates will be calculated using the standard error determined by the Peto method.¹ The survival rate will be compared to historical controls and/or newly published results.

Subjects with follow-up data at the visit of interest will be included in the effectiveness assessments. Change from baseline analyses will include subjects with baseline and follow-up visit data.

Additional exploratory and/or subgroup analyses may also be performed to characterize study outcomes.

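### Device- and therapy-related SAE endpoints are planned as counts without number at risk, censoring rule or confidence interval; if shown as percents of all randomised subjects, they would run modestly low

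*Combined protocol and SAP*

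**What the plan says.** Objectives 2 and 3 (section 7) cover device-related and therapy-related SAEs at three and five years. Each ends with the same plan: "The number of events and subjects with an event will be summarized through each time point". No hypothesis is tested. Section 11.3 repeats the counts for all adverse events.

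Three general rules bear on how those counts would be shown:

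- **Percents.** Section 11.1: "Categorical variables will be summarized by calculating the percent of subjects in each category".
- **Population.** Section 11.2: "All effectiveness and safety evaluations will be based on the ITT population", where ITT means consented and randomised in the pivotal trial. Section 11.3 says that all subjects randomised there "will be included in the safety assessments, unless otherwise noted".
- **Missing data.** Section 11.1: "No imputation for missing data will be performed". The restriction to observed subjects is written for effectiveness only: "Effectiveness analyses will only include subjects with data at the visit of interest".

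Survival is handled differently. Section 11.3 says "The survival distribution will be estimated with a Kaplan-Meier curve", with a 95% CI at three and five years. On numbers, section 6 says "Up to 94 subjects will be enrolled at up to 21 US sites and 5 EU sites" and admits only subjects still actively followed in the pivotal trial.

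**The concern.** A count of subjects with an event through five years can be read only if one knows how many subjects could have shown an event by then. The plan does not say. It also does not say whether a subject who was no longer observed is dropped or counted as event-free; a rule against imputation does not settle this.

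Following the written rules leads most naturally to n/151. Under section 10.8, adverse events are collected from subjects who sign the new consent, with serious and related events between pivotal exit and consent picked up as well. A subject who never signs contributes nothing after the pivotal trial but would stay in an all-randomised denominator. Any such error can only lower the percent, so it favours the device, and it falls mainly on the years that this study was set up to cover. Section 2 names long-term safety as part of the primary purpose of this FDA condition of approval.

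**Working it through.** **1. The precedent.** Appendix F, section 1.9.4.1.1, reports freedom from related SAEs through 12 months as 138/151. The exact (Clopper-Pearson) 95% interval for 138/151 = 91.4% is 85.7% to 95.3%, which matches the printed 91% (86%, 95%). So the pivotal safety figure was a simple proportion of all 151 (13/151 with an event), and it carried an interval.

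**2. Who is unobserved.** Inputs are from Appendix F, sections 1.9.2, 1.9.4.1.3 and 1.9.4.1.4, and protocol section 6.

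- Failed implants: 151 − 147 = 4. The exit list gives 1 + 1 + 2 = 4, which agrees.
- Explanted: 6 exits for explant + 2 subject-initiated exits = 8, which agrees with 8/151.
- Left alive with a system in place: physician-initiated 3 − 1 failed = 2; lost 2 − 1 failed = 1; subject-initiated 10 − 2 explanted − 2 failed = 6. Total 9.
- Check: 22 deaths + 8 + 4 + 9 = 43 exits, as stated.
- Active at datalock: 151 − 43 = 108. With full enrolment, 108 − 94 = 14 are not followed further. This bounds those alive, implanted and unobserved, because some may have died, been explanted or exited by then.

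So 9 to 23 implanted subjects have unobserved time.

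**3. Size, device-related SAEs.** The documents give no later event rates, so these inputs are assumptions, except that first-year risk is the documented 6 subjects with a system-related SAE, over 147. Assumed: later hazard λ of 1-6% per year; death 7% and explant 2% per year; the nine leave evenly over 0-2.25 years; the 14 leave at 2.5 years; no further loss.

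Target: cumulative incidence among the 147, with death and explant as competing events. First-year hazard = −ln(1 − 6/147) = 0.0417, so the total first-year rate is 0.0417 + 0.09 = 0.1317.

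- Year 1: (0.0417/0.1317) × (1 − e^−0.1317) = 3.9%.
- Years 1-5 at λ = 0.03: e^−0.1317 × (0.03/0.12) × (1 − e^−0.48) = 0.877 × 0.25 × 0.381 = 8.4%.
- Five-year total: 12.3%.

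Expected observed subjects with an event come from stepping the same rates through the cohort while removing the leavers. With all 14 lost and λ = 0.03 this is 16.4 subjects, against 147 × 0.1226 = 18.0 with full follow-up.

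| Later hazard per year | Cumulative incidence, 5 years | n/151, all 14 lost | Ratio | Ratio with 147 on both sides | Same, none of 14 lost |
|---|---|---|---|---|---|
| 1% | 6.8% | 6.2% | 0.91 | 0.94 | 0.97 |
| 2% | 9.6% | 8.6% | 0.89 | 0.92 | 0.96 |
| 3% | 12.3% | 10.8% | 0.88 | 0.91 | 0.95 |
| 6% | 19.7% | 17.2% | 0.87 | 0.90 | 0.95 |

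The last two columns isolate lost follow-up: about 3-5% too low if none of the 14 is unobserved and 6-10% if all are. The upper end becomes 11% if every leaver was event-free on leaving. The denominator adds 1 − 147/151 = 2.6%. At 3% per year, lost follow-up costs 0.8 subjects (none of the 14) to 1.7 (all 14). At three years with all 14 lost, n/151 has ratios of 0.94 to 0.91.

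**4. Sensitivity.** Mortality of 5% or 10% moves the ratios by less than 0.01. If risk is mainly late (1% per year to year 3, then 6%), n/151 is about 14-15% low with all 14 lost. If only 74 enrol, it is 13-20% low.

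**5. Therapy-related SAEs.** Two subjects had one by 12 months. With 0.5% or 1% per year assumed later, five-year n/151 against cumulative incidence is 2.5% v 2.8% and 3.8% v 4.3% (all 14 lost), or 2.6% v 2.8% and 4.0% v 4.3% (none). Lost follow-up is worth less than one subject.

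**6. Scale.** The exact 95% interval for 16/151 (10.6%) is 6.2% to 16.6%.

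**The case against.** The planned counts are not wrong in themselves, and the plan never prints 151 for these endpoints. The proviso in section 11.3 leaves room for another denominator, and the rule against imputation could be read as forbidding that an unobserved subject be scored event-free. ITT for safety was a deliberate choice and continues the pivotal convention, so part of the gap (the 2.6%) reflects a choice of population, not missing data. External comparison is planned for survival only, which may explain why only survival has Kaplan-Meier. No test or threshold is affected, and the bias is smaller than the sampling error.

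All of this stands, and it makes the bias conditional and modest. It does not supply a denominator, a number at risk or an interval. Without an interval, a reader cannot see that the bias is the smaller problem.

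A reader might go further and infer that the plan commits to n/151, or that all 151 − 94 = 57 subjects outside this study would be wrongly scored event-free. The documents support neither. The 57 include 22 deaths, 8 explants and 4 failed implants. Death and explant end the risk and are not missing follow-up. Treating all 35 non-death non-participants as lost, with a further 3% loss per year, gives 12-21%, but that counts explanted and never-implanted subjects as lost follow-up.

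**Conclusion.** The point holds as a gap in the analysis plan with a conditional bias, and it should be fixed. The plan gives the long-term SAE endpoints less than it gives survival, and less than the pivotal trial gave its own SAE figure. If the counts become percents of all randomised subjects, the five-year device-related figure is too low by about 3-5% (none of the 14 unobserved) to 6-11% (all 14) in relative terms from lost follow-up, plus about 2.6% if the four failed implants stay in the denominator. At 3% per year the lost follow-up is one to two subjects. For therapy-related SAEs it is negligible.

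The nine leavers and the four failed implants are documented. The 14 is an upper bound given full enrolment, because the datalock date is not stated. Later hazards, mortality, explant rate and exit timing are assumptions. The direction does not depend on those rates, provided that leavers have the same later risk as those who stay. A claim that the plan materially understates device risk would go beyond this evidence.

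**What to change.** In section 11.3, keep the event and subject counts and add wording such as:

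> Each SAE endpoint will also be reported among the 147 successfully implanted subjects as cumulative incidence at 36 and 60 months from implant, with numbers at risk and 95% confidence intervals. Death and complete system explant are competing events; an explant that is itself a qualifying SAE counts as the event. Withdrawal, loss to follow-up and non-enrolment in this study are censored. Events in the four failed implants will be listed separately. The denominator of every simple percent will be printed.

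Death should be a competing event and not ordinary censoring, which would overstate the risk. A second time scale from therapy activation is not needed.

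At the least, print the denominator, the number still followed at 36 and 60 months, and a 95% CI.

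The cost is SAP text and a standard procedure. Appendix C already collects AE onset, original implant, system modification and exit dates. The component options on the System Modification form, as listed, have no explicit explant choice, so the explant date must come from that form's date and primary reason, or an option must be added. The downside is slightly more analysis and a slightly less favourable rate.

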8 SUBJECT SELECTION

8.1 Inclusion Criteria

1. Subjects who were previously implanted with the **remedē** System and participated in the **remedē** System Pivotal Trial
2. In the investigator's opinion, willing and able to comply with all study requirements
3. Signed Institutional Review Board (IRB) / Independent Ethics Committee (IEC) approved informed consent (including Health Insurance Portability and Accountability Act [HIPAA] authorization in the US)

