8.2 Exclusion Criteria

There are no criteria by which a subject would be excluded.

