- **remedē** System assessment including
 - stimulation lead impedance and capture levels on final programmed electrode pair
 - unipolar stimulation lead impedance measurements
 - interrogation including pre and post device settings parameter printouts
- Medical stability assessment prior to PSG (defined as no hospitalizations in the previous 2 weeks)
 - The PSG should not be performed until the subject is medically stable for at least 2 weeks

- PSG in sleep laboratory
 - Must include a minimum of four hours of high quality recording time including a minimum of 2 hours of sleep
- ESS
- Adverse event review and reporting
 - Review events with subject and review medical records since last visit
- Exit the subject from the trial following completion of the visit

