 - Date of Resolution
 - Ongoing, expect eventual resolution
 - Ongoing, stable or chronic condition
 - Death
 - Unknown
- Technical Observation CRF
 - Date of observation
 - Product
 - Physician Programmer
 -
 - Programming wand
 - IPG
 - External IPG
 - Stimulation Lead
 - Therapy delivered by **remedē** System
 - **respiguide**TM
 - Other
 - Model (if applicable)
 - Serial number (if applicable)
 - Comments
- Sleep Study CRF
 - Date
 - Was the subject medically stable?
 - Type of Sleep Study
 - PG
 - PSG

- Total recording time
 - AHI
 - CAI
 - OAI
 - MAI
 - HI
 - Was the subject receiving **remedē** System therapy?
 - Was the subject using concomitant sleep disordered breathing therapy?
 - If yes, select all that apply
 - CPAP
 - Oxygen
 - ASV
 - Bi-PAP
 - Dental appliance
 - Other, specify: _____
- Epworth Sleepiness Scale (ESS) CRF
 - Was ESS completed (Yes/No). If yes:
 - Date
 - Question responses
- Concomitant Cardiac Device CRF
 - Reason for procedure
 - New device
 - Upgrade to new device type
 - Replacement of device
 - Other, specify
 - Date or procedure
 - Type of device
 - Manufacturer and model number
 - Location of device
 - Was interaction testing performed?
 - Date of testing
- System Modification CRF
 - Date
 - Primary reason for system modification
 - Modifications to **remedē** System
 - IPG
 - Not modified
 - Repositioned
 - Replaced
 - Manufacturer, Model, Serial Number

- Implanted (without replacement)
- Stimulation Lead
 - Not modified
 - Repositioned
 - Replaced
 - Manufacturer, Model, Serial Number
 - Capped with replacement
 - Manufacturer, Model, Serial Number
 - Capped without replacement
 - Implanted (without replacement)
- Sensing Lead
 - Not applicable
 - Not modified
 - Repositioned
 - Replaced
 - Manufacturer, Model, Serial Number
 - Capped with replacement
 - Manufacturer, Model, Serial Number
 - Capped without replacement
 - Implanted (without replacement)
- Was system functional following procedure?
 - If no, Reason
 - If yes, Therapy mode
 - If yes, Was interaction testing performed
- Protocol Deviation CRF
 - Date of deviation
 - Visit deviation applies to
 - Type of deviation
 - Visit not performed
 - Visit out of window
 - Assessment out of window
 - Required assessment(s) not done
 - Specify: _____
 - Assessment by untrained / not delegated staff
 - Informed Consent
 - Other, specify: _____
 - Describe the deviation: _____
 - Reason for deviation
- Study Exit CRF
 - Date of study exit

- Reason for study exit

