1.9.2 Patients Studied

The study enrolled 151 central sleep apnea patients who underwent an implant procedure. Of the 151 implant attempts, 147 (97%) were successful. The study endpoints were evaluated based on intent to treat. The patient demographics for the remedē System Pivotal Trial are included in Table 1.

Table 1 **Baseline Demographics**

Baseline Measure	Mean N=151
Age (years)	65
Body Mass Index, kg/m ²	31
Ejection Fraction, %	40
AHI, events/hour	46
CAI, events/hour	28
	n (%)
Male	135 (89%)
Race	
Black or African American	6 (4%)
Unknown	1 (1%)
White	144 (95%)

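### Inclusion criterion 2 ties entry to the full visit and sleep-study burden with no survival/AE-only route, so loss of frail survivors could bias three- and five-year survival upward

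*Combined protocol and SAP*

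**What the plan says.** Inclusion criterion 2 (section 8.1) reads: "In the investigator's opinion, willing and able to comply with all study requirements". Section 8.2 lists no exclusions: "There are no criteria by which a subject would be excluded".

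The requirements are in Table 1 and sections 10.1-10.3. There are office visits at 36, 48 and 60 months, an in-home polygram (PG) at 36 and 48 months, and at 60 months a "PSG in sleep laboratory". Between the office visits, section 6 states: "Subjects will be contacted by phone at 30, 42, and 54 months post implant for survival and adverse event monitoring". Section 10.1 adds a medical-record review to those calls. No route is described for a subject who could take part in the calls but not in the office visits or sleep studies.

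Objective 1 (section 7) is survival, compared descriptively with outside results at three and five years. Objectives 2 and 3 are device- and therapy-related SAEs at the same times. Only Objectives 4 and 5 need sleep studies or the ESS.

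Sections 11.1-11.3 pool this study with the pivotal trial, define ITT as everyone consented and randomized there, estimate survival by Kaplan-Meier, and impute nothing. Effectiveness analyses use only subjects with data at the visit concerned.

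After enrolment, "Visit not performed" is a protocol-deviation type in Appendix C. It is not a listed exit reason there or in section 10.6.

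**The concern.** The criterion sets one threshold for all five objectives, and that threshold is the one needed for the sleep studies. Survival and adverse events can be followed with much less. A living, willing implantee who is housebound or too ill for a laboratory night does not meet the criterion as written, yet an equally frail subject whose decline came after consent stays in follow-up with a missed-visit deviation.

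The analysis consequence lies in the censoring. A pivotal survivor who is not enrolled has no further follow-up and is presumably censored when pivotal follow-up ends; the plan states no censoring rule. Kaplan-Meier then gives that subject the later hazard of those who did enrol. If subjects were declined because they were too ill, that assumption fails in the favourable direction. Survival is Objective 1, the study is an FDA condition of approval, and the estimate will be set beside outside results. No vital-status search or sensitivity analysis for non-enrolled subjects is described. Late SAEs in declined subjects would go unrecorded as well.

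**Working it through.** **No figure to reproduce.** Section 11.4 states that no sample size calculation was made, and the plan gives no expected survival or non-enrolment rate. What follows is illustrative.

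**Inputs from the documents.** The pivotal cohort (Appendix F, 1.9.2): "The study enrolled 151 central sleep apnea patients who underwent an implant procedure". Exits at datalock (Appendix F, Table 6): 3 + 22 + 2 + 10 + 6 = 43, of which 22 were deaths. Still active: 151 − 43 = 108. Enrolment ceiling (section 6): "Up to 94 subjects will be enrolled at up to 21 US sites and 5 EU sites". Follow-up already accrued (section 3): 24 months.

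**Model A.** Assumptions: survival on entry to this study S = 1 − 22/151 = 0.854 (crude, treating datalock as month 24); annual hazard h of 0.05 or 0.08 in enrolled subjects; a fraction q of survivors not enrolled, with hazard HR × h; non-enrolled subjects censored at month 24.

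- Kaplan-Meier targets S·exp(−Th), where T is years after month 24.
- Full follow-up would give S·[(1 − q)·exp(−Th) + q·exp(−T·HR·h)].
- Overstatement = S·q·[exp(−Th) − exp(−T·HR·h)].

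Five years (T = 3):

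- Lowest case, q = 0.05, h = 0.05, HR = 2: 0.854 × 0.05 × (0.861 − 0.741) = 0.5 points.
- q = 0.05, h = 0.08, HR = 3: 0.854 × 0.05 × (0.787 − 0.487) = 1.3 points.
- q = 0.20, h = 0.05, HR = 2: 0.854 × 0.20 × (0.861 − 0.741) = 2.0 points.
- Highest case, q = 0.20, h = 0.08, HR = 3: 0.854 × 0.20 × (0.787 − 0.487) = 5.1 points.

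Three years (T = 1), same extremes: 0.854 × 0.05 × (0.951 − 0.905) = 0.2 points, and 0.854 × 0.20 × (0.923 − 0.787) = 2.3 points.

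At HR = 1 the bracket is zero for every q, h and T.

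**Model B, a check under different assumptions.** All 43 exits fall by month 24, with the 21 exits other than death given half exposure: S24 = 1 − 22/(151 − 10.5) = 0.843, and hazard = −ln(0.843)/2 = 0.085 per year. That average hazard continues in the 108 active subjects, split between f non-enrolled subjects with hazard ratio HR and the rest.

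| Non-enrolled f | HR 2 | HR 3 | HR 5 |
|---|---|---|---|
| 5 | 0.7 | 1.2 | 1.8 |
| 10 | 1.3 | 2.2 | 3.4 |
| 14 | 1.8 | 3.0 | 4.5 |

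Entries are percentage points of upward bias at five years. If enrolled subjects instead follow the average hazard (five-year estimate 0.843 × 0.775 = 0.653), the extremes for f = 14 are 8.5 points too high (0.843 × 14/108 × 0.775, all 14 die) and 2.5 points too low (0.843 × 14/108 × 0.225, all 14 survive).

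**Scale.** With 94 enrolled, about 94 × 0.775 = 73 would be at risk at five years. The Peto 95% half-width is 1.96 × 0.653 × √(0.347/73) = 0.088, or about 9 points.

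**The case against.** Much of the case on the other side stands.

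- **A reader might infer that declined subjects drop out of Objectives 1-3 altogether.** They do not. The ITT set is everyone randomized in the pivotal trial and the data are pooled, so only post-pivotal follow-up is lost.
- **A reader might link the gap of 108 − 94 = 14 to this criterion.** The documents do not support that. The pivotal trial ran at 31 centers (24 in the US, 7 in Europe); this study plans at most 26, chosen for active subjects, resources and willingness. Site non-participation or exits after datalock could explain all 14.
- **A reader might see a contradiction with section 8.2.** An empty exclusion list beside inclusion criteria is ordinary drafting.
- **The criterion is an investigator's opinion, so a lenient site could admit a frail subject.** This is true, and the eligible pool had been under active pivotal follow-up with frequent visits and an overnight study. It lowers the likely number declined, but it leaves the outcome to each site's reading.
- **The calls do not cover everything Objectives 1-3 need.** They fall at 30, 42 and 54 months, whereas reporting is at three and five years. Lead measurements and device interrogation are done only in the office and bear on device-related events. This stands, and it changes the fix.
- **Survival is descriptive, with no hypothesis test, and the scenario biases are smaller than the confidence interval.** This is also true. However, the interval reflects sampling error only, and if frail subjects are the ones declined, the error runs one way.

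**Conclusion.** The point holds as a risk and not as a demonstrated bias. Criterion 2 as written permits sites to decline willing but frail survivors and gives them no reduced follow-up, although the plan tolerates missed visits after consent and already limits effectiveness analyses to subjects with data.

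Under assumed non-enrolment of 5-20% and a hazard ratio of 2-3, five-year survival would be overstated by about 0.5-5 points and three-year survival by about 0.2-2.3 points. Both the number declined and their relative hazard are assumptions; the documents give neither, and with equal hazards the bias is zero. It would be going too far to say that five-year survival is biased upward.

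For SAEs the supportable statement is possible under-ascertainment of late events. The documents do not tie frailty to device- or therapy-related SAEs. This is a low-cost improvement to the entry rule; it does not invalidate the analysis.

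**What to change.** 1. Reword criterion 2 to: willing to be followed at least for survival and adverse events (by phone or record review).
2. Let subjects who cannot attend visits or sleep studies enrol for survival and adverse-event follow-up, with phone or record contact also at 36, 48 and 60 months so that the three- and five-year time points are covered.
3. Record at enrolment which assessments each subject can do. Use all enrolled subjects' follow-up for Objectives 1-3, and those with sleep-study or ESS data for Objectives 4-5.
4. Report pivotal subjects who were active but not enrolled, with reasons, and state where they are censored.

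**Cost.** One reworded criterion, a consent option, an enrolment CRF item, and edits to Table 1 and sections 10.2-10.3 for the added contacts. No new clinical procedure is needed. Reported PG and polysomnogram completion will fall, and device events will be less well ascertained in phone-only subjects, who lack office interrogation; device-related SAE summaries should say how many subjects were followed that way.
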